5.5 ADDITIONAL CONSTRAINTS

Information on prohibited therapies can be found in Section 7.

6. VACCINES

Study vaccine:

The nOPV2 vaccine, live attenuated type 2 modified Sabin strain (S2/cre5/S15domV/rec1/hifi3), is produced by Bio Farma, Indonesia.

Other vaccines:

DTPw-HB-Hib, IPV, PCV and rotavirus vaccine will be provided by the NIP.

6.1 PHYSICAL DESCRIPTION OF THE STUDY VACCINES

The nOPV2 vaccine will be provided to the sites in vials presented as an aqueous yellow-red solution for oral use.

The vaccine will be administered orally.

6.2 CHARACTERIZATION OF VACCINE LOTS

Vials will be filled at concentrations so that each dose of the nOPV2 vaccine will contain no less than $10^{5.0}$ CCID₅₀ (0.1 mL, 2 drops).

6.3 OTHER MEDICATION ADMINISTERED IN THE STUDY

Other vaccines are routine childhood vaccines administered according to the manufacturer's instructions.

6.4 PACKAGING AND LABELING

The nOPV2 vaccine is labelled and packed according to local law and regulatory requirements.

Detailed information on the packaging and labeling is specified in the nOPV2 Handling and Storage Instructions for the study.

6.5 STORAGE AND VACCINE ACCOUNTABILITY

The Investigator (or his/her designee) is responsible for the safe storage of all study vaccines assigned to the clinical site, in a locked, secure storage facility with access limited to those individuals authorized to dispense the study vaccine, and maintained within the appropriate ranges of temperature. All study vaccines must be stored as specified at delivery and in the original packaging.

The nOPV2 vaccine should be stored in a freezer at approximately -20°C ($\pm 5^{\circ}\text{C}$). After thawing, the vaccine can be stored at $+2$ to $+8^{\circ}\text{C}$ for up to 2 weeks. Once opened, a vial must be used within 48 hours, when it expires.

Regular temperature logging of the study vaccine storage room at the clinical site should be performed. In case a deviation in storage conditions should occur, the clinical site must not further dispense the affected study vaccines and notify the Sponsor.

The Investigator is responsible for ensuring that all study vaccines received at the clinical site are inventoried and accounted for throughout the study.

Study vaccines should be dispensed under the supervision of the Investigator, a qualified member of the clinical staff, or by a hospital/clinic pharmacist. The Investigator must maintain accurate records demonstrating date and amount of vaccine administered to and by whom. Study vaccines will be supplied only to subjects participating in the study.

The Sponsor's designated site monitor will periodically check the supplies of study vaccines held by the Investigator or pharmacist to ensure accountability and appropriate storage conditions of all study vaccines used.

Unused study vaccine must be available for verification by the site monitor during on-site monitoring visits. After the last visit of the last subject (LSLV) in the study, any unused vaccine will be returned to the manufacturer, and any used vaccine will be destroyed at the clinical site with the Sponsor's written permission (in this case a certificate of destruction will be provided and filed in the Trial Master File [TMF]).

6.6 RANDOMIZATION AND BLINDING

This is an open-label study.

Allocation of each subject to the 3 treatment groups will be described in a computer-generated randomization schedule prepared prior to start of the study by Assign Data Management and Biostatistics GmbH, [name] using SAS® software (SAS Institute Inc., Cary, NC, USA).

The randomization will apply a 1:1:1 ratio and will be balanced using randomly permuted blocks across the groups.

Blinding of subjects and assessers will not be possible due to the different regimens employed in this study. Laboratory personnel will be blinded to group until such time as the neutralizing antibody assays are complete, and samples from all groups will be randomized for concurrent testing.

6.7 DOSE AND ADMINISTRATION

For all vaccine lots, one dose of vaccine (0.1 ml) is contained in two drops, which are delivered using the dropper supplied with the vaccine.

Other study vaccines provided under the NIP should be administered as per the manufacturer's instructions.

The vaccinees will remain under medical supervision for at least 30 min following the administration of study vaccine.

6.8 COMPLIANCE

All vaccine administrations in the study will be supervised by the Investigator or his/her designee.

7. PRIOR AND CONCOMITANT THERAPY

All therapies (prescriptions and over-the-counter medications) other than the study vaccine administered from informed consent until the last study visit must be recorded in the source documents and in the concomitant therapy section of the electronic case report form (eCRF) (name of the drug, dosage, route and dates of administration).

The Sponsor must be notified in advance (or as soon as possible thereafter) of any instances in which prohibited therapies are administered.

There will be no restrictions in using concomitant therapies except for any medication that has a potential effect on the immune system in the opinion of the Investigator.

Infants will receive routine vaccinations according to the Dominican Republic NIP which will be provided by the NIP.

8. ASSESSMENTS

8.1 TIMING OF ASSESSMENTS

An overview of the timing of vaccine administration and assessments is given in the Time and Events Schedules.

Parent(s)/guardian(s) will be given a full explanation of the nature of the study and written informed consent (approved by the local ethics committee) will be obtained from parent(s)/guardian(s) according to local requirements before any study-related assessment will be carried out.

Adverse events and the administration of concomitant medication will be monitored continuously from informed consent until the last study-related activity at Day 187 (Group A), Day 194 (Group B) or Day 208 (Group C). Solicited AEs will be collected for 7 days following each dose, unsolicited AEs will be collected until 28 days following each study vaccination and SAEs/IMEs will be collected from the date of informed consent signature throughout the study.

After informed consent process has been completed, the assessments will proceed as outlined in the Time and Events Schedules. The subjects will be kept under medical supervision for at least 30 minutes after administration of the study vaccine. The subjects will then receive routine vaccinations outlined in the Time and Events Schedule.

An electronic diary card and a thermometer will be distributed to parent(s)/guardian(s) and their use will be explained. Paper diary cards could be used as backup.

Unscheduled visits can be planned, for instance to obtain additional information to ensure the safety of the subject. Additional blood and urine samples may be taken at the discretion of the Investigator if deemed necessary for safety observation.

Findings made during unscheduled visits should be reported in the source documents and in the designated sections of the eCRF.

8.2 IMMUNOGENICITY

8.2.1 *Immunogenicity Variables*

Blood samples for the determination of neutralizing type 2 poliovirus antibodies will be taken at the time points specified in the Time and Events Schedules. Neutralizing antibodies against poliovirus will be determined using a sero-neutralization assay.

Detailed descriptions of the collection, handling, transport and processing of the blood samples will be included in the laboratory manual.

Samples that remain after protocol-specific assessments have been performed may be used for further exploratory work on polio, including cryofreezing for future immunological studies. No human DNA or RNA analysis will be performed.

8.2.2 *Immunogenicity Criteria*

For an overview of endpoints, see Section 3.

The following endpoints will be based on neutralizing type 2 poliovirus antibody titers:

- Seroconversion: defined as seropositive (titer $\geq 1:8$) in those initially seronegative, or among those initially seropositive, a minimum 4-fold higher titer (and seropositivity) than that which is expected due to maternal antibodies, using an exponential model to estimate the maternally-derived antibody titers at post-vaccination time points from the pre-vaccination time point, assuming a half-life of 28 days. Seroconversion will be computed from Day 0 for all subjects.
- Seroprotection: defined as poliovirus serotype-specific titers $\geq 1:8$.
- Geometric mean and median titers.
- Geometric mean fold-rise

8.3 SAFETY EVALUATIONS

The safety assessment in this study will be based on AEs.

Adverse events will be monitored continuously from the time of informed consent signature until Day 187 (Group A), Day 194 (Group B) or Day 208 (Group C) (180 + 7 days after the last administration of the study vaccine). At regular intervals during the study, at the on-site visits and over the phone, parents will be asked non-leading questions to determine the occurrence of any AEs.

For detailed definitions and reporting procedures of AEs, see Section 11.

Solicited AEs will be recorded by the subjects' parent(s)/guardian(s) for 7 days following each dose of study vaccine using a diary card. These will be reviewed by the Investigator during the phone calls or on-site visits that will be scheduled with the subject's parent(s)/guardian(s) 7 days after each dose. In addition, unsolicited AEs will be collected during regular study phone calls and on-site visits for 28 days after each vaccination. Any SAEs and IMEs will be collected from the date of the informed consent signature throughout the study.

8.4 EXPLORATORY EVALUATIONS

Not applicable.

8.5 APPROPRIATENESS OF MEASUREMENTS

The assessments which will be made in this study are either standard or are scientifically justified.

Each biological assay contains a reference material used as a control. Additional re-test of some samples may be conducted to ascertain the presence of temporal variability in assay results.

9. STUDY TERMINATION/COMPLETION

9.1 STUDY COMPLETION

9.1.1 Subject Completion

A subject will be considered to have completed the study if all study-related procedures have been completed for them 28 days after the last study vaccination (i.e, Day 35 [Group A], Day 42 [Group B] or Day 56 [Group C]) and they are not withdrawn before the final study safety follow-up 6 months after their last study vaccination (i.e, Day 187 [Group A], Day 194 [Group B] or Day 208 [Group C]).

9.1.2 Study Completion Date

The study completion date is considered to be the date on which the final serologic analysis is available for the purpose of assessing the primary immunogenicity objective.

9.2 REMOVAL OF SUBJECTS FROM STUDY OR INVESTIGATIONAL PRODUCT

9.2.1 Removal from Study

Parents(s)/guardian(s) have the right to withdraw subjects from the study at any time for any reason, including personal reasons. A subject can be withdrawn without giving a reason. The Investigator should however try to find out why a subject is withdrawn from the study and document the reason for withdrawal in the source documents and on the eCRF.

Subjects **may** be withdrawn from the study in the event of:

- A severe AE or a SAE;
- Difficulties in obtaining blood or other samples;
- Failure of the subject and/or subject's parent(s)/guardian(s) to comply with the protocol requirements or to cooperate with the Investigator.

Subjects **must** be withdrawn from the study in the event of:

- Withdrawal of consent by parent(s)/guardian(s);
- For safety reasons, if, in the Investigator's opinion, in the best interest of the subject.

In the event of a subject being withdrawn from the study, the monitor and Sponsor should be informed: in the event of withdrawal due to an SAE (for details on AE reporting see Section 11), the Sponsor should be notified within 24 hours; in the event of withdrawal for other reasons, the Sponsor should be notified within 2 days from the event.

If there is a medical reason for withdrawal, the subject will remain under the supervision of the Investigator until satisfactory health has returned.

Subjects who are withdrawn from the study prior to completion of the scheduled study procedures for any reason (e.g. AE, withdrawal of consent) should be invited to complete

the assessments as much as possible: as long as the subjects' parent(s)/guardian(s) consents, all relevant assessments of the day on which the subject withdrew from the study should be completed, at least those related to safety. In case of an AE, the appropriate follow-up will be done.

Subjects who are withdrawn from the study will not be replaced.

9.2.2 *Removal from Investigational Product*

Removal from investigational product administration concerns subjects who do not receive a complete study vaccination schedule as planned per protocol. A subject who is withdrawn from further study vaccine administration need not necessarily be withdrawn from the study as further study procedures or follow-up may be performed (safety or immunogenicity) if planned in the study protocol.

Information pertaining to premature discontinuation of the study vaccine will be documented in the eCRF. The Investigator will document whether the decision to discontinue further vaccination was made by the subjects' parent(s)/guardian(s) or the Investigator, and which of the following possible reasons was responsible for withdrawal:

- SAE/IME.
- AE.
- Other (specify).

10. **STATISTICAL METHODS**

10.1 **STATISTICAL ANALYSIS**

All statistical analyses will be performed by Assign Data Management and Biostatistics GmbH, [name] using SAS® software (SAS Institute Inc., Cary, NC, USA) under the supervision and responsibility of the Sponsor.

This document describes the basic elements of the statistical analysis to be performed. All statistical methods shall be detailed in a Statistical Analysis Plan (SAP) that will be finalized before database lock.

Unless otherwise specified, descriptive statistics include mean, standard deviation, median, maximum, minimum, and range for continuous variables and the number and percentage in each group for categorical variables.

Unless specified otherwise in the SAP, statistical tests and CIs will be computed using a two-sided 5% significance level. Exact (Clopper-Pearson) CIs will be used for univariate summaries of dichotomous variables, and Miettinen-Nurminen score-based CIs will be used for rate differences.

10.1.1 ***Study Populations***

The following populations will be considered for analysis:

- The Enrolled Population is defined as all subjects for whom informed consent is provided, regardless of the subject's randomization and vaccination status.
- The TVP is defined as all subjects who received at least 1 dose of study vaccine.
- The Reactogenicity Population is defined separately for each dose (dose 1 and dose 2) as those subjects who received the respective dose and who completed the diary card.
- The Per-Protocol (PP) Population consists of all eligible study participants who are in the TVP, who provided an evaluable pre-vaccination serum sample, and who received all of the immunizations at the interval scheduled for the group to which they were allocated and excludes those subjects who received any therapy that could significantly affect the subject's immune status and those subjects who met criteria outlined in Section 5.3. The PP Population will be adapted by time point to allow subjects to contribute data to PP analyses until such time as they become disqualified. All deviations and violations occurring in the study will be reviewed prior to database lock and classified as either minor or major.

Unless specified otherwise, the TVP will be used for safety analysis and analysis of demographics. The Reactogenicity Population will be used to summarize incidence of solicited events. Immunogenicity analyses will be primarily conducted in the PP Population.

10.1.2 *Analysis Sequence*

A final analysis of immunogenicity outcomes will be conducted upon completion of assays and reconciliation of data, which may be in advance of the completion of safety follow-up. This will include an analysis of baseline characteristics and disposition. Safety data will be described upon completion of the study, including all safety follow-up.

10.1.3 *Initial Characteristics Data of the Subject Sample*

Descriptive statistics will be provided per group for demographic (e.g., age, weight, race, gender) and other initial subject characteristics (e.g., medical and surgical history, concomitant diseases). Demographics will be compared using Chi-squared and Fisher's exact test for categorical variables, and Kruskal-Wallis and pairwise Wilcoxon test comparisons for continuous variables.

Prior and ongoing medical history will be coded with the Medical Dictionary for Regulatory Activities (MedDRA), summarized and listed.

Prior and concomitant medications will be coded using the WHO_DRUG Dictionary, summarized, and listed.

Disposition, including receipt of doses, inclusion in study populations and reasons for dropout will be summarized and listed, and a CONSORT diagram will be prepared.

10.1.4 *Immunogenicity Data*

For an overview of primary and secondary endpoints, see Section 3.

For descriptive analyses, at each pre-and post-vaccination time point where neutralizing antibody titers are obtained:

- Cumulative seroconversion rates (with 95% exact CIs) will be computed.
- Seroprotection rates (with 95% exact CIs) will be computed.
- Geometric mean and median neutralizing antibody titers (with 95% CIs) will be computed. Mean titers will be estimated on the \log_2 scale using likelihood-based estimation, using a normal error assumption, to accommodate censoring at assay lower limit of quantification (LLOQ)/upper limit of quantitation (ULOQ), then reverse-transformed to obtain the geometric mean and corresponding CI. The median \log_2 titer will be paired with bootstrap-based CIs.
- Fold-rises will be computed as the mean of differences (subsequent time point minus prior time point) on the \log_2 scale, then reverse-transformed along with the corresponding 95% CI. Cumulative fold rises will be computed relative to the expected level of maternally-derived antibodies in accordance with the seroconversion definition, and secondarily for post-dose-2 samples, from the level attained following the first dose, with the pre-dose-2 serum sample.
- Plots of the reverse cumulative distribution of antibody titers will be generated for each group.
- Additional figures will include boxplots and bar charts of immune responses (seroconversion, seroprotection rates, GMTs with accompanying CIs).

Subgroup analyses, to be detailed in the SAP, will include analyses such as according to baseline immune status and according to gender.

Comparative immunogenicity analyses will be limited to baseline immunity (seroprotection rate, GMTs) and post-dose-2 time points corresponding to the study objectives, and post-dose-1 results will be descriptive only.

Comparisons for binary variables (seroconversion, seroprotection) will be based on the difference in rates (shorter interval minus standard interval), and paired with two-sided 95% Miettinen-Nurminen CIs for the difference. For the primary endpoint, non-inferiority of a shorter-interval regimen to the standard regimen will be declared if the lower bound of the CI is greater than -10%. For other comparisons, a statistically significant difference will occur if the CI excludes 0%.

Comparisons of GMTs will arise from geometric mean titer (GMT) ratios computed via a linear model of the \log_2 titers which incorporates left/right censoring at LLOQ/ULOQ. With the exception of the comparison of baseline immunity, a separate model will be fit for each comparison, limited to the groups involved in the comparison. For baseline immunity, a global F-test for a difference will be conducted and, if significant at level 0.10, the model will be used to produce pairwise comparisons of each group. The reverse-transformed two-sided 95% CI for the GMT ratio will be paired with the p-value corresponding to the F-test for a difference between groups. A difference between groups will be indicated if the CI excludes a GMT ratio of 1.

Median titers will be analyzed on the \log_2 scale, and paired with two-sided 95% bootstrap CIs. A difference between groups will be indicated if the interval excludes a difference of 0.

Fold-rises will be compared using standard normal distribution-based two-sample methodology on the \log_2 scale, followed by a reverse transformation. If an excess of titers reaches assay limits of quantitation, subgroup analyses will be conducted among those subjects with samples within the quantifiable range. A difference between groups will be indicated if the two-sided 95% CI for the ratio of geometric mean fold rises (reverse-transformed difference of differences) excludes a value of 1.

10.1.5 Safety Data

For an overview safety endpoints, see Section 3.

Safety parameters will generally be tabulated and analyzed descriptively, in the TVP, according to the actual administration interval received. Solicited events will be summarized in the Reactogenicity Population, according to the actual administration interval received. Additional analyses will aggregate across all groups following each dose and overall, including solicited events following each dose independently and overall (TVP, all groups combined), unsolicited events at any time point (TVP, all groups); the SAP will provide further detail.

Analyses described below will be performed for solicited and unsolicited AEs by severity, as well as for SAEs and IMEs. Events will only be considered as solicited if onset occurs within 7 days of a vaccination. All events with onset between Days 8 and 28 post-vaccination will be considered unsolicited. Any SAEs and IMEs will be collected from the date of the informed consent signature throughout the study and will be analyzed with unsolicited events, as well as separately.

The original terms used in the designated sections of the eCRFs by Investigators to identify AEs will be fully described and coded according to the MedDRA.

All AEs will be summarized by group, type, by post-vaccination timepoint and overall (regardless of timing of onset), by severity and occurrence in relation to vaccination, and overall, separately for solicited and unsolicited AEs. Determination of causal association to the study vaccine will be assigned using the individual causality assessment algorithm published by WHO in 2013¹⁸. All SAEs, IMEs and unsolicited AEs will be deemed eligible for causality assessment by the investigator or the safety monitor. After applying the Adverse Event Following Immunization (AEFI) causality algorithm, the SAE, IME or unsolicited AE will be classified as consistent or inconsistent with causal association to immunization; those which meet the definition of causality will be defined as reactions (respectively, serious adverse reactions [SARs], important medical reactions and unsolicited adverse reactions). Events with insufficient or conflicting evidence to make a determination of association will be deemed indeterminate according to the algorithm.

Separate tables and listings will be created for subjects who died, discontinued the study vaccine due to an AE, or experienced an SAE. Summaries, listings, and narratives may be provided, as appropriate. Unsolicited AEs occurring within 28 days of any vaccine administration will be summarized, as will any data obtained on SAEs or IMEs reported during the safety follow-up.

Abnormal physical exam findings and vital signs will be summarized.

10.1.6 *Exploratory*

Not applicable.

10.1.7 *Missing Data*

The reasons for any missing data will be ascertained and appropriate statistical methods will be used to accommodate these absences in the analyses of the study data that minimize potential biases and maximize efficiency conditional on the causes for data being missing. Data values that are identified by quality control procedures to be spurious will not be used in final analyses of the study data.

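### Sections 10.1.1 and 10.1.5 name different populations for solicited events, so the pooled solicited rates can fall below the group rates they aggregate

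*Combined protocol and SAP*

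**What the plan says.** Protocol section 10.1.1 (Study Populations) defines the two populations that matter here.

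- TVP: "The TVP is defined as all subjects who received at least 1 dose of study vaccine". Neither a second dose nor a diary is required.
- Reactogenicity Population: set up separately for dose 1 and dose 2, "as those subjects who received the respective dose and who completed the diary card".

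The same section then gives the rule for solicited events, with no exception attached: "The Reactogenicity Population will be used to summarize incidence of solicited events".

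Section 10.1.5 (Safety Data) repeats it: "Solicited events will be summarized in the Reactogenicity Population, according to the actual administration interval received". The next sentence introduces supplementary pooled work: "Additional analyses will aggregate across all groups following each dose and overall". Its list includes "solicited events following each dose independently and overall (TVP, all groups combined", and it closes with "the SAP will provide further detail".

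Three other places bear on the point. Sections 5.3 and 5.4 describe infants who get no second dose yet may remain under follow-up. Sections 8.3 and 11.6 have adverse events asked about at visits and calls as well as through the diary. Section 10.1.7 leaves missing data to unspecified suitable methods.

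**The concern.** The incidence of solicited events after each dose is a secondary safety endpoint (section 3.2), and the plan gives it two populations. The choice matters because solicited events are collected mainly through the diary. An infant without a completed diary stays in a literal TVP denominator but has no systematic route into the numerator. An infant who never had dose 2 cannot have an event after dose 2, yet belongs to the TVP.

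The pooled Reactogenicity rate is a weighted average of the three group rates and must lie between the lowest and the highest. A pooled TVP rate need not. A report could show three group rates and a pooled rate below all of them, with nothing to tell the reader that the denominator had changed.

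The infants without dose 2 are also not a random subset. Under section 5.4, one reason for withholding it is a severe or serious event judged consistent with a causal link to dose 1.

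**Working it through.** **Plan's own figure.** There is none to reproduce. The protocol states no expected solicited-event rate, diary-completion rate or safety precision. Its only loss allowance is in section 10.2: 270 evaluable raised to 300 per group, so 1 − 270/300 = 10%. That covers loss from the evaluable population in the seroconversion sample size. It is not a diary-loss rate and is at most a loose guide.

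**Who is in each denominator, read literally**

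| Pooled rate | Reactogenicity Population | TVP |
|---|---|---|
| After dose 1 | dose 1 and its diary | all with dose 1, with or without a diary |
| After dose 2 | dose 2 and its diary | also those with no dose-2 diary and those with no dose 2 |
| Overall | in at least one dose-specific set | also those with no completed diary at all |

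In the overall row, an infant with dose 1 only and a dose-1 diary has real data and belongs in both columns. The missing-dose problem is confined to the dose-2 rate.

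**Formula.** Let p be the incidence among diary completers for a dose. Let m be the share of the TVP outside that dose's Reactogenicity Population, and q the incidence recorded in that share by other routes. Then:

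- TVP rate = p(1 − m) + qm
- shortfall = m(p − q)

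If q = p the shortfall is 0. If q = 0 it is mp, a relative understatement of exactly m. For infants who never had dose 2, q = 0 after dose 2 by definition.

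**Limiting case, q = 0.** Both p and m are assumptions, shown as a range. Cells give the TVP rate.

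| p | m = 1% | m = 2% | m = 5% | m = 10% |
|---|---|---|---|---|
| 10% | 9.9% | 9.8% | 9.5% | 9.0% |
| 30% | 29.7% | 29.4% | 28.5% | 27.0% |
| 50% | 49.5% | 49.0% | 47.5% | 45.0% |

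The shortfall runs from 0.1 to 5.0 percentage points. In counts, with 900 infants and m = 10%, 810 are completers: 243/810 = 30.0% against 243/900 = 27.0%.

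**Partial capture.** With p = 30%, m = 5% and half the events recorded by other routes (q = 15%), the TVP rate is 0.30 × 0.95 + 0.15 × 0.05 = 29.25%, half the shortfall of the limiting case.

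**The case against.** The strongest reply is that nothing in the protocol says an infant without a diary is counted as event-free.

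- **Other capture.** Sections 8.3 and 11.6 have the investigator ask about adverse events at every contact, a contact is scheduled about seven days after each dose, and a paper diary is available as backup. Some solicited-type events in non-completers would be recorded. This stands: it makes p(1 − m) a limiting case.
- **Bias in completers.** Completer-only rates can be biased too if completion depends on symptoms. This also stands, and is a reason to keep a TVP table as a sensitivity analysis.
- **Wording.** A summary after each dose may be meant for recipients of that dose. That reading would remove infants without dose 2 but not those without a diary, so it answers only part of the point.
- **Deferral.** Detail is left to the SAP, and the TVP label may be deliberate. But the two sections still conflict, and neither the deferral nor the general missing-data wording says which denominator applies.
- **Reach.** The affected tables are additional and descriptive, with no test attached. This stands.

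A reader might go further and infer that the plan scores these infants as event-free, that reactogenicity will be understated, and that dose 2 will falsely look better tolerated than dose 1. The documents do not support this. They contain no such scoring rule and no rates from which to compare the two doses. Nor do they support changing the denominator for unsolicited events, because the pooled unsolicited summary covers events at any time point and is not a per-dose rate.

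**Conclusion.** The inconsistency is on the page: section 10.1.1 assigns solicited incidence to the dose-specific Reactogenicity Population, and section 10.1.5 assigns the pooled solicited summaries to the TVP. Followed literally, the pooled rates can be lower than the group rates they aggregate, by a relative amount of up to the unobserved share of the TVP.

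That upper limit assumes that the unobserved infants stay in the denominator and contribute no events. The shortfall shrinks as more events are recorded at visits and calls, and it vanishes if capture is equal or the denominator is restricted to infants with the dose and the diary. The actual size cannot be known from the documents.

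The summaries by interval received, which carry the secondary safety endpoint, and the primary immunogenicity analysis are not affected. The contradiction itself is certain; the size and practical effect of the dilution are not.

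**What to change.** In section 10.1.5, change the population for the pooled solicited summaries from the TVP to the Reactogenicity Population pooled over groups, and carry the same wording into the SAP:

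- per-dose rates: infants who had that dose and completed its diary;
- overall rate: infants in at least one dose-specific Reactogenicity Population.

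If a TVP version is wanted, present it as a sensitivity table. It should show how many infants lacked the dose and how many lacked the diary, and should include solicited-type events captured outside the diary.

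Leave the denominator for unsolicited events as it is.

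The cost is one sentence in 10.1.5 and its counterpart in the SAP. No new data are needed. Because the SAP is to be completed before the database is locked, the denominator can be settled before the final safety results are known.
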